8.2.1. Inclusion criteria

Patients must meet all of the following inclusion criteria to be eligible for inclusion in the study:

- Histologically confirmed metastatic renal cell cancer patients who have already been using targeted therapies for up to 1 months as 3rd line treatment
- Patients 18 years and older than 18 years
- Evidence of a personally signed and dated informed consent document indicating that the patient (or a legal representative) has been informed of all pertinent aspects of the study.

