Adverse events will be summarized using the CTCAE.4.03 coding system. Event rates for single adverse events will be calculated based on the total number of patients valid for safety. Adverse events will be categorized according to relation, seriousness, CTCAE grade (version 4.03), and discontinuation of therapy, action taken and outcome. Special attention will be paid to serious adverse events and unexpected or unlisted ADRs.

Category counts and frequencies (percentages) will be calculated for overall tolerability.

Since the enrollment is after the initiation of the treatment, some information will be collected and analyzed retrospectively.

The best overall response is the best response recorded from the start of the study treatment until the end of treatment taking into account any requirement for confirmation.

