6. RATIONALE AND BACKGROUND

Background

Metastatic renal cell carcinoma (mRCC) is the most common malignant tumour of the kidneys. Targeted therapies, which were recently introduced in the treatment of mRCC, have become the standard treatment in these patients [1]. With improved survival rate and a tolerable side effect profile, Tyrosine Kinase Inhibitors (TKIs) have largely replaced conventional immunotherapies worldwide. [2,3]

These developments have led to new research to identify the effects of these therapies on the quality of life and the treatment-related side effects.

In Turkey, due to reimbursement conditions defined by authority, cytokine (interferon alpha) treatment is the standard treatment in the first-line therapy [4]. Therefore, the data on quality of life from the pivotal studies with standard TKI treatment doesn't reflect QoL of the patients treated with TKIs as second or third line treatment in Turkey.

Rationale

TKI therapy is used after interferon alpha in Turkey due to current reimbursement status.

Therefore, the data on quality of life from the pivotal studies with standard TKI treatment doesn't reflect the QoL status of the patients treated with TKIs as second or third line treatment in Turkey. In this study, the clinical outcomes and the impact on quality of life of targeted treatments following TKIs will be explored. To our knowledge, since there is no similar reimbursement condition in the world placing IFN as the first line standard treatment, this will be the first study evaluating the QoL status with targeted therapies used as 3rd line treatment in this setting.

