8. RESEARCH METHODS

8.1. Study design

This is a multi-center post-marketing observational study. It has been defined according to the NUTS (Nomenclature of Territorial Units for Statistics: Nomenclature d'unités Territoriales Statistiques, French) criteria, which is a regional classification, created in order to reduce interregional disparities in socio-economic analysis of the regions, and to produce data comparable to that of the European Union (EU). Turkey has been divided into 12 NUTS regions depending on the economic, social, cultural, and geographical aspects, and the population size. In this study, patients with metastatic renal cell carcinoma from centers in 12 NUTS regions of Turkey will be included, who meet the inclusion criteria. Since this is a non-interventional observational study, there is no specific follow-up protocol. In this study, approximately 152 patients planned to be recruited in a year and followed-up 12 months.

This is a multi-center post-marketing observational study. In this study, patients with metastatic renal cell carcinoma from centers in 12 NUTS regions of Turkey will be included,

who meet the inclusion criteria. Since this is a non-interventional observational study, there is no specific follow-up protocol.

Presuming that there are 1800 patients with metastatic renal carcinoma in Turkey, the minimum sample size was calculated as 152.

There will be a total of 25 centers in various cities of Turkey.

The centers will consist of medical oncology clinics.

In this study, the patient follow-up period is 12 months. Each patient will be followed up to 5 times; the data will be collected at baseline, the 3rd, 6th, 9th and 12th months according to the routine practice. Additionally, every patient will be followed-up once for survival follow-up in order to assess the overall survival before the site close out visit. Survival follow-up will be performed via telephone visit or site visit if exist.

Because of the observational nature of the study, there is no predefined treatment protocol. The participating physician will continue to treat the patients at his/her own discretion. Frequency of visits will be continued per physician's preference.

The patients will be asked to fill in the quality of life questionnaire (FKSI-15, EQ5D-3L, FKSI-DRS) on each visit.

The assessment of the side effects will be based on the "Common Terminology Criteria for Adverse Events". The CTCAE V.4.03 will be used.

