8.3. Variables

The outcome variables for the objective(s) are time to treatment failure (from start of treatment to progression or permanent discontinuation), overall survival (from start of treatment to the date of last follow up or death), therapeutic response to therapy based on response evaluation criteria in solid tumors (RECIST version 1.1), and safety (type, incidence, severity of adverse events graded by the National Cancer Institute [NCI] CTCAE V.4.03)

Variable	Role	Data source(s)	Operational definition
Age, gender, height, weight, blood pressure, socio-demographic characteristics	Baseline characteristic	Medical Records	
Concomitant diseases	Baseline Characteristic	Medical Records	
Medication	Baseline Characteristic	Medical Records	
Histopathological findings	Baseline Characteristic	Medical Records / Pathology Reports	
Surgical Operations	Baseline Characteristic	Medical Records	
The cytokine (interferon alpha) usage in the first-line treatment, TKI usage in the 2 nd line treatment and the dosage and the duration of the treatment	Baseline Characteristic	Medical Records	
Metastatic features	Baseline Characteristic	Medical Records	
MSKCC risk factors	Baseline Characteristic Follow-up Characteristic	Medical Records	
3 rd line treatment	Baseline Characteristic Follow-up Characteristic	Medical Records	

	Close-out Characteristic		
The performance score before the second and third-line treatment		Medical Records	
The quality of life questionnaire (FKSI-15, EQ5D-3L, FKSI-DRS) on each visit	Baseline Characteristic Follow-up Characteristic Close –out Characteristic	Patient interview	
Blood pressure		Patient diary	
Other treatment during follow-up, if any, the dose and the duration	Follow-up Characteristic	Medical Records	
Treatment of the side effects, interruption of the treatment, dose reduction, dose-elevation	Baseline Characteristic Follow-up Characteristic	Medical Records	
Duration of PFS, OS and ORR	Follow-up Characteristic Close-out Characteristic	Medical Records	

Schedule Procedure	Initial visit	Follow-up 3.month	Follow-up 6.month	Follow-up 9.month	Follow-up 12.month	Survival Follow-up
Demographic data	X					
Histopathological Findigs	X					
Medical history	X					
Previous therapy of mRCC	X					
MSKCC Risk Factors	X	X	X	X	X	
Surgical Operations	X					
Metastases Information	X					
FKSI-15, EQ5D-3L, FKSI-DRS Questionnaire	X	X	X	X	X	
Evaluation of PFS,OS and ORR		X	X	X	X	
Concomitant medication	X	X	X	X	X	
Visit date	X	X	X	X	X	

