For those safety events that are considered serious or that are identified in the far right column of the table above that are reportable to Pfizer within 24 hours of awareness, the investigator is obligated to pursue and to provide any additional information to Pfizer in accordance with this 24-hour timeframe. In addition, an investigator may be requested by Pfizer to obtain specific follow-up information in an expedited fashion. This information is more detailed than that recorded on the case report form. In general, this will include a description of the adverse event in sufficient detail to allow for a complete medical assessment of the case and independent determination of possible causality. Any information relevant to the event, such as concomitant medications and illnesses must be provided. In the case of a patient death, a summary of available autopsy findings must be submitted as soon as possible to Pfizer or its designated representative.

Reporting period

For each patient, the safety event reporting period begins at the time of the patient's first dose of 3rd line treatment or the time of the patient's informed consent if s/he is already exposed to 3rd line treatment, and lasts through the end of the observation period of the study, which must include at least 28 calendar days following the last administration of a drug under study; a report must be submitted to Pfizer Safety (or its designated representative) for any of the types of safety events listed in the table above occurring during this period.

If the investigator becomes aware of a SAE occurring at any time after completion of the study and s/he considers the SAE to be related to 3rd line treatment, the SAE also must be reported to Pfizer Safety.

Causality assessment

The investigator is required to assess and record the causal relationship. For all AEs, sufficient information should be obtained by the investigator to determine the causality of each adverse event. For AEs with a causal relationship to 3rd line treatment, follow-up by the investigator is required until the event and/or its sequelae resolve or stabilize at a level acceptable to the investigator, and Pfizer concurs with that assessment.

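### The quality-of-life baseline is an on-treatment value, so the study can describe quality of life during 3rd-line therapy but not the change from before it that the title and rationale imply

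*Combined protocol and SAP*

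**What the plan says.** - **Entry.** The first inclusion criterion (section 8.2.1) takes patients "who have already been using targeted therapies for up to 1 months as 3rd line treatment". The abstract, under Data Analysis, adds: "Since the enrollment is after the initiation of the treatment, some information will be collected and analyzed retrospectively".
- **Questionnaires.** Section 8.1 states that "the data will be collected at baseline, the 3rd, 6th, 9th and 12th months according to the routine practice". In section 8.3 the row "The quality of life questionnaire (FKSI-15, EQ5D-3L, FKSI-DRS) on each visit" has baseline, follow-up and close-out roles, and its source is patient interview. The schedule in the same section marks "FKSI-15, EQ5D-3L, FKSI-DRS Questionnaire" from the initial visit onward and has no earlier column.
- **Consent.** Section 9.1 requires written consent before any study-specific activity.
- **Aim.** The primary objective in section 7 is to measure quality of life with 3rd-line targeted therapy. The title speaks of effects on quality of life, and section 6 says "the clinical outcomes and the impact on quality of life of targeted treatments following TKIs will be explored".
- **Analysis.** Section 8.5 states that no hypothesis is tested, and section 8.7 calls the analyses mainly explorative and descriptive. Section 8.6 lists repeated-measures ANOVA and the Friedman test in general terms. No section defines a quality-of-life baseline or a change from it.
- **Limitations.** The contents list a limitations section as 8.9. In the text supplied, 8.9 is a not-applicable entry for other aspects.

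**The concern.** Quality of life is the first primary objective. A reader will take a value called baseline, in a study whose title promises effects, as the state before treatment. Here it is the state after some days or weeks of treatment, and the number of days differs between patients. Early toxicity or early symptom relief may already be in it.

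If toxicity lowers scores early, a later comparison with the initial form looks too flat, and the treatments look better tolerated than they were. If symptoms ease early, part of a benefit is hidden. Patients enrolled on day 2 and on day 30 also do not share a common reference point. A larger sample removes none of this.

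**Working it through.** **Step 1. Can a pre-treatment value exist under the current text?** Sections 8.2.1 and 3 place enrolment after the first dose. Section 9.1 rules out study questionnaires before consent, and the schedule in 8.3 starts at the initial visit. Retrospective collection does not fill the gap, because the source for quality of life is patient interview, not records. The one status score sought from before 3rd line is a different item, taken from medical records: "The performance score before the second and third-line treatment". So no pre-treatment quality-of-life value is available for any patient.

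**Step 2. Does the safety section change this?** Section 10 starts the reporting period at the patient's "first dose of 3rd line treatment or the time of the" patient's consent, the latter for those already exposed. The first alternative would fit someone who consents before treatment, whom 8.2.1 does not admit. The clause sits uneasily with 8.2.1 and the abstract, but it schedules no questionnaire.

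**Step 3. Does the plan's own figure bear on the point?** Section 8.5 gives 152 patients from a population of 1800, a precision of 7.6 and 95% confidence. Assume a proportion of 0.5 and read 7.6 as a half-width in percentage points:

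- n0 = 1.96² × 0.25 / 0.076² = 166.3
- n = 166.3 / (1 + 165.3/1800) = 152.3, which agrees with 152.

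This is the precision of a proportion. It contains no quality-of-life effect or standard deviation, so the distortion cannot be sized from it.

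**Step 4. Illustration of size. All inputs except the one-month window are assumptions.** Let the effect on quality of life build as 1 − exp(−kt) after first dose, with k = ln 2 / h for half-life h in days. Let enrolment be uniform over days 0 to 30.

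- Mean share of the eventual effect already present at the first form: 1 − (1 − exp(−30k)) / (30k)
- Share for a patient enrolled on day 30: 1 − exp(−30k)

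For h = 14, 30k = 1.485 and exp(−1.485) = 0.226. The mean share is 1 − 0.774/1.485 = 0.479, and the day-30 share is 0.774.

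| Assumed half-life (days) | Mean share, uniform enrolment | Share if enrolled on day 30 |
|---|---|---|
| 7 | 68% | 95% |
| 14 | 48% | 77% |
| 30 | 28% | 50% |
| 60 | 15% | 29% |

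The shares refer to an effect that moves in one direction to a plateau. With opposing early effects, or later decline from progression, they do not carry over to an observed change at month 3 or month 12.

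**Step 5. Can time on treatment be derived?** The schedule records visit date and 3rd-line treatment at the initial visit, and section 8.3 times treatment failure and overall survival from the start of treatment. Days from first dose to each form should therefore follow from data already collected.

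**The case against.** The strongest reply is that the plan never sets out to estimate a change from before treatment. The objective is measurement on therapy, there is no hypothesis, and the analysis is descriptive. This stands. Levels and their course from enrolment to month 12 meet the objective, so a reader who infers that the primary quality-of-life objective fails goes further than section 7 allows. What remains is that the title and section 6 claim more than the design gives, and that the initial form has a baseline role without qualification.

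Second, a pre-dose form would not show that 3rd-line therapy caused a change. There is one cohort and no comparator, and section 8.2 describes patients who have progressed after a TKI. This also stands. The form would make a before-to-during change available, but not attribution.

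Third, enrolling patients already on treatment is disclosed, and it fits section 9.4, which separates prescription from the decision to include. Enrolment after prescription but before the first dose would keep that separation too, so this supports the current choice without ruling out the alternative.

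Fourth, a change now comes late. Version 2.1 is dated 09 March 2016. Section 5 plans first visits from May 2015 to December 2016, so on those dates about 10 of 19 months had passed. Patients already enrolled cannot supply a pre-dose form, and those who can will be selected by time and site logistics. This stands, and it is why the main analysis should not be confined to that subset.

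**Conclusion.** The concern holds in a limited form. Every initial quality-of-life form is an on-treatment value, taken up to one month after first dose, and nothing elsewhere in the plan repairs this. The study can report quality of life on 3rd-line therapy and its course from enrolment. It cannot report the change from before to during therapy, which the words effects and impact suggest.

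The 15% to 68% range rests on assumed exponential onset, half-lives of 60 to 7 days and uniform enrolment over days 0 to 30. It shows that the lost part could be material and is not an estimate. A reader might infer that reported changes are too small by a known share, or that the treatments will look better tolerated than they are. The documents give no quality-of-life course, variability or distribution of enrolment days, so neither size nor direction can be stated. A reader might also take section 10 as provision for pre-dose enrolment, but it is only a safety-reporting clause.

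**What to change.** 1. **Remaining recruitment.** Widen the first inclusion criterion to admit patients from prescription of 3rd-line therapy, before first dose, up to one month after first dose. Ask for the first questionnaires before first dose where possible. Reconcile the abstract's Data Analysis text, section 8.2.1 and the reporting period in section 10. The analysis sets in section 8.7 already require at least one dose, so patients who never start would drop out of them.
2. **All patients.** Derive days from first 3rd-line dose to each questionnaire, and analyse quality of life longitudinally on that axis, for example with a mixed model, instead of by visit number alone. Label post-dose initial forms as on-treatment quality of life at enrolment, and summarise the days on treatment at that form.
3. **Before-to-during change.** Report it as a descriptive supplementary analysis in patients with a pre-dose form, without causal attribution. For the rest, restate effects and impact as on-treatment quality of life, and state the limitation where the contents announce a limitations section.

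**Cost.** A minor amendment with IRB/IEC approval (section 9.3), plus approval of any consent-form change (section 9.1). Item 2 should need no new data. The pre-dose subset will be small, imprecise and drawn from later enrolment, so it supplements the all-patient analysis and does not replace it.

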8.2.2. Exclusion criteria

Patients meeting any of the following criteria will not be included in the study:

- Patients with contraindications for the use of the study medications
- Patients with (suspected) pregnancy or in lactation period
- Patients who are investigational site staff members directly involved in the conduct of the trial and their family members, site staff members otherwise supervised by the Investigator, or patients who are Pfizer employees directly involved in the conduct of the trial.
- Participation in other studies involving investigational drug(s) (Phases 1-4) within 4 weeks before included in the current study.

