PFS, OS and ORR evaluation during 3rd, 6th, 9th and 12th months performed according to RECIST version 1.1, additionally, every patient will be followed-up once for survival follow-up in order to assess the overall survival before the site close out visit. Survival follow-up will be performed via telephone visit or site visit if exist.

ORR: The best overall response is the best response recorded from the start of the study treatment until the end of treatment taking into account any requirement for confirmation. The patient's best overall response assignment will depend on the findings of both target and non-target disease and will also take into consideration the appearance of new lesions. Furthermore, depending on the nature of the study and the protocol requirements, it may also require confirmatory measurement.

PFS: The length of time during and after the treatment of a disease, that a patient lives with the disease but it does not get worse. In a clinical trial, measuring the progression-free survival is one way to see how well a new treatment works.

OS: 1 year Overall Survival (OS), defined as the time from the start of 3rd line treatment until death or 1 year due to any cause (measured at the end of follow-up).

Data Sources

The source of the data will be the electronic or the written patient records of the participating centers. The patient's data can be accessed through a patient file. In the centers, both systems can be used in conjunction. The data can be accessed using both systems.

Sample Size

This is a multi-center, national, non-interventional/observational study. In this study, patients with metastatic renal cell carcinoma who meet the inclusion criteria will be included from centers in 12 NUTS regions of Turkey. Since this is a non-interventional observational study, there is no specific follow-up protocol. In this study, approximately 152 patients will be evaluated.

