Outcome Measures are overall objective response rate (ORR) [Time frame: from enrollment to objective response], progression-free survival (PFS) [Time frame: from enrollment to disease progression or death, whichever occurs first], overall survival (OS) [Time frame: from enrollment to death or the end of the study duration] and probability of patient survival at 1 year [Time frame: from enrollment to 1 year]

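### The 4-week investigational-drug exclusion is counted back from inclusion rather than from the start of 3rd line treatment, so the study-free interval it guarantees before the first dose shrinks from 28 days to about 0

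*Combined protocol and SAP*

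**What the plan says.** Section 8.2.2 lists as an exclusion "Participation in other studies involving investigational drug(s) (Phases 1-4) within 4 weeks before included in the current study". The reference date is inclusion in this study.

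Section 8.2.1 admits patients who "have already been using targeted therapies for up to 1 months as 3rd line treatment". The abstract (section 3, Data Analysis) confirms the order of events: "Since the enrollment is after the initiation of the treatment, some information will be collected and analyzed retrospectively". Inclusion therefore follows the first dose of the treatment under evaluation.

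Several outcomes are counted from that first dose:

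- Section 8.3 defines "time to treatment failure (from start of treatment to progression or permanent discontinuation") and "overall survival (from start of treatment to the date of last follow up or death").
- The abstract's 1-year overall survival is "defined as the time from the start of 3rd line treatment until death or 1 year due to any cause".
- Best overall response, in section 3 and again in section 8.7, is taken from the start of study treatment.

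Section 8.1 uses a different origin in its list of outcome measures, for example "progression-free survival (PFS) [Time frame: from enrollment to disease progression or death, whichever occurs first"]. Response rate and overall survival are also given an enrolment origin there.

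No section sets an interval free of investigational drugs before the start of 3rd line treatment.

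**The concern.** An exclusion window of this kind can protect only the period it covers. Here it covers the 4 weeks before inclusion, and part or all of those weeks may already be time on 3rd line treatment. The interval before the first dose is then protected only by what is left over.

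Two things follow. First, for outcomes that start at the first dose, residual activity of an agent taken in another study could be credited to, or held against, the 3rd line treatment. Response rate is a primary objective and overall survival a secondary one; time to treatment failure is an outcome variable in section 8.3 but not a listed objective. Second, eligibility depends on an administrative date. The same treatment history can pass or fail according to when the consent form was signed.

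**Working it through.** **Plan's own figure.** The documents give no figure for the interval before treatment, so there is nothing to reproduce. The sample size of 152 does not depend on this criterion.

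**Inputs**

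- Window: 4 weeks = 28 days, counted back from inclusion (section 8.2.2).
- t = days on 3rd line treatment at inclusion, from 0 up to 1 month (section 8.2.1). The documents do not say whether a month is 28, 30 or 31 days.
- g = days between the end of participation in another study and the first 3rd line dose.

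**Step 1: the rule as written.** The time from the end of the other study to inclusion is g + t. The patient is eligible if g + t is at least 28, that is, if g is at least 28 − t. The smallest permitted gap before the first dose is therefore 28 − t.

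| t (days on treatment at inclusion) | Guaranteed study-free days before first dose, 28 − t |
|---|---|
| 0 | 28 |
| 7 | 21 |
| 14 | 14 |
| 21 | 7 |
| 28 | 0 |
| 30 | −2 |
| 31 | −3 |

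The last two rows apply only if 1 month is read as a calendar month. The rule would then allow another study to overlap the first 2 or 3 days of 3rd line treatment. If 1 month means 4 weeks, the minimum is 0.

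**Step 2: same history, different eligibility.** As an illustration, take two patients who each left another study 10 days before their first 3rd line dose (g = 10).

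- Included on day 5: g + t = 10 + 5 = 15, below 28, so excluded.
- Included on day 25: g + t = 10 + 25 = 35, above 28, so eligible.

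**Step 3: the rule with the anchor moved.** If the same 28 days are counted back from the first dose, the condition is that g is at least 28, and t drops out. Both patients in step 2 are then treated alike (10 is below 28), and every included patient has the same 28-day guarantee.

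**Step 4: which outcomes are exposed.**

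| Outcome | Start of clock | Does the 4-week window fully precede it? |
|---|---|---|
| Time to treatment failure (8.3) | Start of treatment | Only if t = 0 |
| Overall survival (3, 8.3) | Start of treatment | Only if t = 0 |
| Best overall response (3, 8.7) | Start of treatment | Only if t = 0 |
| Response rate, PFS, overall survival (8.1) | Enrolment | Yes |
| Adverse events in already-exposed patients (10, Reporting period) | Informed consent | Yes, taking consent as the point of inclusion |
| Baseline quality of life (8.3 schedule) | Initial visit | Yes |

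**The case against.** The case for leaving the criterion alone is substantial, and much of it limits the point.

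- **Adverse events.** A reader might infer that toxicity carried over from another study would be counted as 3rd line toxicity during the unprotected days. Section 10 does not support this: for patients already exposed, safety reporting starts at consent, and the schedule in section 8.3 collects adverse events from month 3. The window precedes that period.
- **Time origins.** Section 8.1 counts response, PFS and overall survival from enrolment, and this is the only explicit start given for PFS. On that origin the 4 weeks do precede the clock. This stands, although the treatment under evaluation has still begun earlier. The conflict between section 8.1 and sections 3, 8.3 and 8.7 is a separate defect and must be reconciled in its own right.
- **Timing of response assessment.** Scheduled assessments begin at month 3, well after any permitted participation in another study. This weakens carry-over into response but does not exclude it.
- **Recorded history.** A reader might infer that an intervening investigational agent would go unreported. The schedule in section 8.3 collects previous mRCC therapy, medical history and concomitant medication at the initial visit, so that does not follow. But recording is not exclusion, and section 8.7 plans no analysis by recent investigational exposure.
- **The 3rd line requirement.** An extra anticancer agent between the 2nd and 3rd lines would arguably make the current therapy a later line and the patient ineligible. This removes many cases. It leaves, for example, a study of the 2nd line TKI itself or of a non-cancer drug.
- **Intent.** The documents state no purpose for the criterion. It could be meant to keep the retrospective on-treatment period free of other study drugs, since 4 weeks roughly matches the permitted month. That reading is coherent, and the change proposed below serves it too.
- **Participation, not dosing.** The criterion refers to taking part in a study. The last dose may have been earlier, so 28 − t is a worst case for the drug-free interval.

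**Conclusion.** The mismatch is real, and it follows from the two eligibility sections and the stated order of treatment and enrolment. The guaranteed study-free interval before 3rd line treatment is 28 − t days, from 28 down to about 0. It goes below 0, by 2 to 3 days, only if 1 month is a calendar month. The consequence is confined mainly to outcomes counted from treatment start, on the definitions in sections 3, 8.3 and 8.7.

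It is tempting to assume that inclusion dates are spread evenly over the month and to quote a percentage of patients with a short gap or an overlap. The documents do not support that. They give no distribution of inclusion dates and no count of patients coming from other studies, and a short guaranteed minimum matters only for those patients. The number is unknown, probably small and possibly zero. No bias has been shown and none can be estimated. The study is descriptive and section 8.5 states that it tests no hypothesis. This is a minor point, worth correcting because correction is cheap.

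**What to change.** Reconcile the anchor in section 8.2.2 with section 8.2.1. Keep the sponsor's own 4-week length, count it back from the first dose of 3rd line treatment, and also cover the time from that dose to inclusion. Possible wording: *taking part in another investigational-drug study (Phases 1–4) at any time from 4 weeks before the first 3rd line dose up to inclusion*. Stating what 1 month means in section 8.2.1 would settle the calendar-month ambiguity.

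First enrolment was planned for May 2015 and this version is dated March 2016, so some patients may have entered under the existing rule. For them, record the end date of any participation in an investigational-drug study. Then repeat the response-rate, time-to-treatment-failure and overall-survival summaries without those who fail the re-anchored rule, as a sensitivity analysis. This avoids removing enrolled patients and shows whether the two eligibility rules make any difference.

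The cost is one amended sentence, one e-CRF date and possibly a few otherwise eligible patients. The sample size of 152 does not change, and no visit, test or treatment is added.
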